8 PROCEDURES AND METHODS

8.1 INFORMED CONSENT

As the study Sponsor, Edwards Lifesciences must approve any modifications to the Informed Consent Form prior to submission to the institutional review board (IRB), and/or FDA (as required). A sample Informed Consent Form is provided in Appendix A – Sample Informed Consent Form.

Once the patient's physician has determined the patient's eligibility for the study, the background of the proposed study, and the benefits and risks of the procedures and study should be explained to the patient. The patient (or the patient's legal representative) must sign the institution's approved Informed Consent Form prior to participation. Failure to provide informed consent renders the patient ineligible for the study.

The consent form will be written in the native language of the patient and administered only by the Investigator or IRB approved personnel who speak the native language of the patient. The Principal Investigator or delegated person administering the consent must sign and date the Informed Consent Form to indicate that the purpose, risks and benefits of the study were explained to the patient and that their signature was witnessed.

The Investigator will retain the original consent form, a copy will be filed in the patient's medical record, and a copy of the Informed Consent Form will be provided to the patient.

Informed consent MUST be obtained prior to any study related procedures. Signed informed consent forms must be retained by the study site for verification during on-site monitoring visits.

8.2 PATIENT ENROLLMENT

All patients enrolled under this Revision L of the Clinical Protocol will be consented, treated and followed according to the requirements described herein. Patients enrolled under previous versions of the Clinical Protocol will not be required to re-consent under Revision L and will be followed according to the requirements of the protocol version to which they were consented.

A Screening/Enrollment Log, provided by the Sponsor, will be maintained at the study site to document the screening and enrollment of all patients assessed for study participation. The screening of patients qualifying for this study should be carried out in a sequential, prospective manner, such that all patients are offered the possibility of participating in the study, and are therefore evaluated according to the selection criteria defined in this protocol. Patients who are consented to participate in the study but do not fulfill enrollment criteria, will be considered “screen failures” and will not count towards the overall enrollment cap. The reason for “screen failure” will be recorded on the screen failure log. Reasons for screen failure may include but are not limited to:

- Qualifying patient is not offered an opportunity to participate by Investigator
- Qualifying patient refuses to participate
- Investigator opts for alternative therapy for qualifying patient
- Potential patient fails the screening criteria

All patients assessed for study participation that have signed the informed consent form will be entered on the screening log. These patients will be assigned a sequential patient ID number by the study Sponsor. The patient ID number together with the patient initials shall be used to identify the patient on all study-related documents.

Patient will be considered “provisionally enrolled” when they have signed the informed consent form agreeing to participate in the study and have been deemed eligible for study participation by meeting the study criteria (Sections 7.2-7.3). A patient will be considered “enrolled” at the time of skin incision to introduce the FORMA System into the body.

8.3 BASELINE EVALUATION

1. Informed consent will be obtained from all patients who have been determined to be eligible study candidates and agreed to participate in the study.
2. Patient demographics and medical history (includes 12 months prior hospitalizations including emergency department (ED) visits, paracentesis)
3. Clinical Evaluation (includes vital signs, concomitant medical treatments, edema grading, ankle circumference measurements, weight and height) and NYHA classification
4. Administration of Health Status Questionnaires (e.g., SF-12, KCCQ)
5. Administration of Six Minute Walk Test (6MWT)
6. Administration of Katz Index of Independence in Activities of Daily Living (ADL)
7. Administration of Canadian Study of Health and Aging (CSHA) Clinical Frailty Scale[®]

8. Administration of Patient Edema Questionnaire
9. Administration of Patient Preference Survey
10. Modified Rankin score (mRS) *
11. Clinical Laboratory Tests
 - a. The following lab tests shall be done within 30 days of the scheduled implant procedure:
 - i. Troponins and cardiac enzymes (CK-MB) - *MI within 30 days of the scheduled implant procedure is an exclusion from study participation*
 - b. The following lab tests shall be done \leq 2 weeks before implant procedure:
 - i. CBC and platelet count
 - ii. Complete metabolic panel
 - iii. Liver panel including gamma-glutamyl transferase (GGT)
 - iv. Serum Creatinine and eGFR
 - c. The following lab tests shall be done \leq 48 hours before the implant procedure:
 - i. β HCG for women who are not sterile or post-menopausal- *positive result is an exclusion from study participation.*
 - ii. INR and PTT/aPTT
12. Standard 12-lead Electrocardiogram (ECG)
13. Comprehensive Transthoracic Echocardiogram (TTE must be collected per Echocardiography Acquisition Protocol) ⁶.
14. Transesophageal Echocardiogram (TEE), including but not limited to transgastric views.
15. All candidates must have pre-implant procedure imaging (e. g., Computed Tomography (CT) Angiogram), that captures the anatomy of the subclavian and axillary veins, superior vena cava, tricuspid valve and sub-valvular structures/anatomy, right atrium and right ventricle.
16. Invasive Hemodynamic Monitoring/Right Heart Catheterization that should include, but is not limited to, right atrial pressure (RAP), PAP, right ventricle pressure (RVP), cardiac output (CO), and PVR measurements.⁷
17. Candidates with cardiac leads may also have a venogram (subclavian and axillary veins) as part of pre-implant procedure imaging, if venous patency cannot be determined by pre-procedure CT.
18. Candidates with pacemaker leads must have interrogation of their device to determine pacing stability and pacing dependency. Pacemaker dependency is defined as continuous ventricular stimulation without any pacemaker inhibition by

⁶ If candidate had new cardiac procedure since baseline TTE and TEE that were submitted for screening, the TTE and TEE should be repeated and resubmitted.

⁷ If the screening echo confirms the PAP meets the study criteria, the right heart catheterization/hemodynamic assessment at the baseline evaluation may be waived.

spontaneous cardiac activity determined during the last interrogation within 180 days.

19. Coronary angiogram

*mRS will be conducted at baseline for all patients with a history of stroke. For patients who experience a stroke during the study, mRS will be conducted closest to 90 days post event. It is recognized that an assessment of stroke is incomplete without an appropriate measurement of the disability resulting from the stroke, hence, mRS closest to 90 days post event will be used to assess clinical disability. Every effort should be made to have a neurologist or neurology fellow perform the neurological assessments, or alternatively, a trained research team member certified in stroke assessment. mRS can be obtained by a certified research team member via phone interview with the patient or caregiver member if the patient is unable to visit the research office.

Baseline data to be collected will include but is not limited to the information listed in the following table:

Table 6 - Baseline Evaluation

| General Information | Clinical Information | Laboratory Measurements |
|---|--|---|
| 
 • Inclusion/exclusion evaluation • Informed consent • Age • Gender • Height • Weight | 
 • Local Heart Team determination • Patient demographics • Medical history (e.g., EuroSCORE, STS Score) /prior cardiovascular interventions / surgeries / 12-month prior hospitalizations and paracentesis • Vital signs (Blood pressure, heart rate) • Edema grading & ankle circumference measurements • Concomitant Medications and doses • NYHA classification • Echocardiographic measurements (TTE & TEE), tricuspid regurgitation & heart function • CT • Coronary angiogram • Venogram (in patients with cardiac leads) if required | 
Within 30 days of procedure:
 
 • Date of blood draw • Troponin¹ and CK-MB¹ 
Within ≤ 2 weeks of procedure:
 
 • Date of blood draw • Serum Creatinine & eGFR • WBC • RBC • Hematocrit • Hemoglobin • Platelets • ALT/SGPT • AST/SGOT • Bilirubin • LDH • GGT • ALP • Albumin • Sodium & potassium • Urea 
Within ≤ 48 hours of procedure:
 
 • INR & PTT/aPTT • βHCG, if applicable² |

| General Information | Clinical Information | Laboratory Measurements |
|---------------------|---|-------------------------|
| | 
 • Interrogation of pacemaker leads • Invasive Hemodynamic Monitoring/Right Heart Catheterization including pressure measurements • ECG results • Six minute walk test • Katz Index (ADL) test • CSHA Frailty scale • KCCQ & SF-12 questionnaires • Edema Questionnaire • Preference Survey • mRS (if applicable) | |

1. MI within 30 days of the scheduled implant procedure is an exclusion from study participation
2. A positive result is an exclusion from study participation

8.4 ANTIPLATELET / ANTICOAGULATION THERAPY

Recommendations for antiplatelet/anticoagulation therapy are detailed below and in Table 7. Alternative anticoagulation/antiplatelet regimens may be considered according to the needs of individual patients or a hospital's standard practice; these will not constitute a protocol deviation. For study patients on an existing dual antiplatelet therapy or with known hypersensitivity to the required medications, the investigator will determine the antiplatelet/anticoagulation therapy.

Patients on anticoagulation (e.g. Warfarin or Apixaban) will discontinue use prior to implant procedure. Patients not on anticoagulation prior to the procedure should receive Aspirin (at least 75 – 100 mg daily) and Plavix (300 mg or per investigator's preference) prior to implant procedure.

Heparin will be administered at procedure start, before introduction of any catheter into the vasculature. During the procedure, ACT will be monitored and recorded on source documentation. Heparin will be administered during the procedure as needed to maintain the patient's ACT at ≥ 250 sec. The sheaths may be removed when ACT level is appropriate (e.g., reaches < 150 sec) after implantation of the study devices.

Post procedure, patients on Aspirin and Plavix should continue receiving dual anti-platelet therapy through the 6 month follow up visit. The antiplatelet regimen past the 6-month follow-up visit will be determined at the Investigator's discretion.

Patients on anticoagulation (e.g. Warfarin or Apixaban) will continue with their prescribed anticoagulation medications post implant procedure through the 6-month follow-up visit. See Table 7.

Table 7 – Summary of Recommended Concomitant Medical Therapy

| Visit | Patients on anticoagulant* prior to implant procedure | Patients Not on anticoagulant* prior to implant procedure |
|--------------------------------|---|--|
| Pre Procedure | Discontinue anticoagulant | Start Aspirin and Plavix |
| Intra-Procedure | IV Heparin | IV Heparin |
| Post-Procedure through Month 6 | Resume anticoagulant | Continue Aspirin and Plavix |

*Anticoagulant: e.g., Warfarin or Apixaban

8.5 DEVICE PREPARATION

A description of device preparation and use is provided in the IFUs, (See Report of Priors/Clinical Investigator's Brochure). Investigators must be familiar with the information described in the IFU prior to use of the FORMA System.

An Edwards Representative that has been trained on the preparation of the FORMA System will be in attendance at all implant procedures.

8.6 IMPLANT PROCEDURE

The implant procedure shall be performed under general anesthesia with hemodynamic monitoring in an operating room, catheterization lab or hybrid operating room with fluoroscopic, angiographic and echocardiographic imaging capabilities. The use of cardiopulmonary bypass is not required.

The following study procedures will occur during the implant procedure:

1. Safety Evaluation
2. Transesophageal Echocardiogram
3. Ventriculogram Imaging
4. Invasive Hemodynamic Monitoring/Right Heart Catheterization including right atrial pressure measurements pre and post implant
5. Heparin administration to achieve (and maintain) an ACT of ≥ 250 sec during the implant procedure

Patients will be monitored in the operating room as needed with special attention to hemodynamic condition and cardiac rhythm. Subsequent monitoring of patients will be continued in the recovery room or ICU.

The date of the implant procedure will be considered as Day 0 for the purpose of determining specified time intervals for the follow up visit for the implanted and non-implanted cohorts.

Procedure data to be collected will include but is not limited to the information listed in the following table:

Table 8 – Procedure Information

| General Information | Clinical Information | Laboratory Measurements |
|--|--|--|
| 
 • Hospital admission date • Patient identification number • Names of Interventional Cardiologist & Access Management Physician • Procedure date • Access site • Timing of implant procedures • FORMA System identification & disposition | 
 • Fluoroscopy duration & contrast volume • Heparin administration & ACT levels • TEE measurements, tricuspid regurgitation & heart function • Ventriculogram Imaging • Invasive Hemodynamic Monitoring/Right Heart Catheterization and pressure measurements performed • Adverse events • Device malfunction | 
Within 24 -48 hours post implant:
 
 • Troponin¹ and CK-MB¹ • WBC • RBC • Hematocrit • Hemoglobin • Platelets • ALT/SGPT • AST/SGOT • Bilirubin • LDH • GGT • ALP • Albumin • Sodium & potassium • Urea • Serum creatinine & eGFR • PTT/aPTT & INR |

1. If an elevation was noted post implant (within 48 hours), tests must be repeated three times or until not clinically significant

8.6.1 ANTIBIOTIC PROPHYLAXIS

It is recommended that all recipients be prophylactically treated for endocarditis to minimize the possibility of infection.

8.6.2 CONTRAST MEDIA

Careful management of contrast media is required for these patients. Accurate measurement of the dye used during the implant procedure shall be captured in the appropriate case report form.

8.6.3 DAY 1 POST-IMPLANT

The following study procedures will be performed 24-48 hours post implant procedure:

1. Clinical Evaluation
2. Safety Evaluation
3. Clinical Laboratory Tests
 - a. CBC and platelet count
 - b. Complete metabolic panel
 - c. Liver panel
 - d. PTT/aPTT and INR
 - e. Serum creatinine and eGFR
 - f. Troponins and cardiac enzymes (CK-MB)
4. Standard 12-lead ECG

8.6.4 DISCHARGE

The following procedures will be performed prior to discharge from the hospital/unit:

1. Clinical Evaluation and Concomitant Medications
2. Safety Evaluation
3. Clinical Laboratory Tests
 - a. CBC and platelet count
 - b. Complete metabolic panel
 - c. Liver panel
 - d. INR and PTT/aPTT
 - e. Serum creatinine and eGFR
 - f. Troponins and cardiac enzymes (CK-MB), only required if an elevation was noted post implant (within 48 hours)
4. Standard 12-lead ECG
5. Administration of Patient Edema Questionnaire
6. Comprehensive Transthoracic Echocardiogram per echo core lab acquisition protocol

7. Modified Rankin score (mRS) mRS will be conducted for all patients who had a stroke since their last assessment. It is recognized that an assessment of stroke is incomplete without an appropriate measurement of the disability resulting from the stroke, hence, mRS closest to 90 days post event will be used to assess clinical disability. Every effort should be made to have a neurologist or neurology fellow perform the neurological assessments, or alternatively, a by a trained research team member certified in stroke assessment. mRS can be obtained by a certified research team member via phone interview with the patient or caregiver member if the patient is unable to visit the research office.

Discharge data to be collected will include but is not limited to the information listed in the following table:

Table 9 – Discharge Information

| General Information | Clinical Information | Laboratory Measurements |
|--|--|--|
| 
 • Discharge date & location discharged to (e.g., home) • Weight | 
 • Clinical evaluation (mobility, edema grading & ankle circumference measurements, ascites, access site) • Vital signs (Blood Pressure, Heart Rate) • TTE measurements, tricuspid regurgitation & heart function • ECG results • Concomitant medications and doses¹ • Edema Questionnaire • Adverse events • mRS (if applicable) | 
 • Date of blood draw • Troponin and CK-MB, if applicable • WBC • RBC • Hematocrit • Hemoglobin • Platelets • ALT/SGPT • AST/SGOT • Bilirubin • LDH • GGT • ALP • Albumin • Sodium & potassium • Urea • Serum creatinine & eGFR • INR & PTT/aPTT |

1. *No changes in diuretics are allowed for at least 3 months post procedure unless patient presents with severe hypotension.*

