3.1 POTENTIAL RISKS

The potential risks of use of the FORMA System are similar to those encountered with standard cardiac catheterization and use of anesthesia and have been listed in two categories below. First, there are the potential complications associated with the overall procedure including standard cardiac catheterization and the use of anesthesia. Second, there are the additional potential risks associated with the use of the FORMA System. Estimated occurrence rankings of the potential risks are provided in the Sample Informed Consent Form in Appendix A.

[REDACTED]

Risks related to the overall procedure including standard cardiac catheterization and the use of anesthesia may include, but may not be limited to, the following:

- abnormal lab values;
- access site AV fistula or pseudoaneurysm;
- allergic reaction to anesthesia or to contrast media;
- anemia;
- angina;
- arrhythmia;
- bleeding;
- cardiovascular or vascular injury including perforation, obstruction, or dissection of valvular structures that may require intervention, including access sites;
- conduction system injury (defect) which may require replacement or implantation of a pacemaker (permanent or temporary);
- death;
- dyspnea (e.g., orthopnea);
- electrolyte imbalance;
- embolization including air, particulate, calcific material, or thrombus;
- exercise intolerance or weakness;
- fever;
- heart failure;
- heart murmur;
- hematoma;
- hemorrhage requiring transfusion or intervention;
- hypertension/hypotension;
- infection, including septicemia and endocarditis;
- inflammation;
- leaflet damage;
- myocardial infarction;
- pain or changes at the access site;
- paralysis;
- pericardial effusion/cardiac tamponade;
- permanent disability;
- pleural effusion;
- pulmonary edema;
- renal failure;
- renal insufficiency;
- reoperation;
- restenosis;
- retroperitoneal bleed;

- skin burn;
- syncope;
- systemic peripheral ischemia/nerve injury;
- thromboembolic events, stroke, transient ischemic attack, clusters, or neurological changes;
- wound dehiscence, delayed or incomplete healing.

In addition to the risks listed above, additional potential risks associated with the use of the FORMA System may include, but may not be limited to, the following:

- cardiac arrest;
- cardiac dysrhythmias requiring replacement or implantation of a pacemaker (temporary or permanent);
- cardiac failure/low cardiac output;
- cardiogenic shock;
- chordal damage, rupture;

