- damage to or interference with function of pacemaker or implantable cardioverter-defibrillator (ICD);
- deterioration of native valve (leaflet tear/tearing, leaflet retraction, leaflet thickening, leaflet stenosis, or other);
- device degeneration;
- device explants;
- device migration, malposition or embolization requiring intervention;
- device thrombosis requiring intervention;
- emergency cardiac surgery;
- hemolysis;
- leakage around device;
- non-emergent reoperation;
- nonstructural implant dysfunction;
- papillary muscle damage;
- pneumothorax;
- pulmonary artery outflow tract obstruction;
- structural deterioration (wear, fracture, calcification, shaft creep, or other);
- thromboembolism (permanent or transient pulmonary and/or neurological events);
- transvalvular flow disturbances;
- valvular regurgitation;
- ventricular or atrial wall damage, abrasion, or perforation;
- worsening of heart failure;
- worsening of valvular insufficiency.

There may be other risks that are unknown at this time. All safety events will be collected and reviewed throughout the entire study and follow-up period. The Investigators will be notified of any additional risks identified that could affect the health, safety or welfare of the study patients.

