7.2 INCLUSION CRITERIA

The Investigator has the responsibility of screening potential patients to determine if the patients meet all the inclusion criteria. The following are requirements for entry into the study:

1. Age \geq 18 years old
2. Symptomatic severe (Stage D) functional, tricuspid regurgitation (per applicable guidelines)
3. Symptomatic despite medical therapy; patient must be on diuretic therapy.
4. The local site Heart Team determines that the patient is appropriate for transcatheter tricuspid repair
5. Patient is willing and able to comply with all specified study evaluations and provides written informed consent.

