12.2 REPORTING PROCEDURE

Study patients will be carefully monitored during the clinical study (starting from the signing of informed consent) for any possible adverse event. All adverse events will be fully investigated by the Investigator. Appropriate treatment for the patient will be initiated while the study follow up continues. Adverse events will be followed until they are adequately resolved or explained.

The Investigator will attempt to assess the involvement of the investigational device and / or study procedure in the adverse event. All observations and clinical findings, including the nature or the seriousness, will be documented on the appropriate case report form (CRF). The investigator will classify the adverse events (AEs) based on the definitions in section 12.3

Adverse events will be assessed by the Investigator for causality to the investigational device or index procedure as defined in MEDDEV 2.7/3 revision 3:

Not related: Relationship to the device or procedures can be excluded when:

- The event is not a known side effect of the product category the device belongs to or of similar devices and procedures
- The event has no temporal relationship with the use of the investigational device or the procedures
- The serious event does not follow a known response pattern to the medical device (if the response pattern is previously known) and is biologically implausible
- The discontinuation of medical device application or the reduction of the level of activation/exposure - when clinically feasible – and reintroduction of its use (or increase of the level of activation/exposure), do not impact on the serious event
- The event involves a body-site or an organ not expected to be affected by the device or procedure
- The serious event can be attributed to another cause (e.g. an underlying or concurrent illness/ clinical condition, an effect of another device, drug, treatment or other risk factors)
- Harms to the subject are not clearly due to use error
- In order to establish the non-relatedness, not all the criteria listed above might be met at the same time, depending on the type of device/procedures and the serious event

Unlikely: The relationship with the use of the device seems not relevant and/or the event can be reasonably explained by another cause, but additional information may be obtained.

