#### **4. ANALYSIS POPULATIONS**

This clinical study will enroll 60 patients. This sample size was established based on typical sample sizes for early feasibility studies and no statistical justification was utilized.

It was decided that from an analysis perspective, data from the first 30 patients (patient enrolled before Rev L) and second 30 patients (Patient enrolled under Rev L and after) will be analyzed together and also separately by sub-groups of before rev L and rev L and after, where applicable.

The analysis population will be grouped into three analysis cohorts that in total comprise all the patients in whom the study procedure has been attempted (vascular access obtained) in this study. The analysis cohorts are defined below:

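### The 3-month diuretic restriction excepts only severe hypotension, which conflicts with the instruction to treat adverse events and, on the stricter reading, puts a sponsor-approval step before non-emergency diuretic changes

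*Protocol*

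**What the plan says.** Protocol 8.6.4, Table 9 footnote 1, states: "No changes in diuretics are allowed for at least 3 months post procedure unless patient presents with severe hypotension". The same sentence stands under Table 10 (Protocol 8.7) and as footnote 3 of Table 13, the summary of required study procedures. Neither document adds another exception.

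Protocol 7.2 requires of every patient: "Symptomatic despite medical therapy; patient must be on diuretic therapy". Protocol 3.1 lists "electrolyte imbalance" and "renal insufficiency" among the procedural risks and "worsening of heart failure" among the device risks.

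On adverse events, Protocol 12.2 says: "Appropriate treatment for the patient will be initiated while the study follow up continues". It does not mention diuretics. Protocol 14.3 defines a deviation as conduct not in line with the protocol. It requires sponsor approval beforehand, except to protect a patient in an emergency, and requires every deviation to be reported even when it is medically justified.

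On who is bound, Protocol 8.2 says that patients from before Rev L "will be followed according to the requirements of the protocol version to which they were consented". SAP 4 divides the study into the "first 30 patients (patient enrolled before Rev L) and second 30 patients (Patient enrolled under Rev L and after".

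**The concern.** The restriction is narrower than the protocol's own list of risks. Its patients are all on diuretics and symptomatic despite therapy. Inside the 3 months the protocol checks creatinine, eGFR and the metabolic panel on day 1, at discharge and at 1 month, and grades edema at discharge and at 1 month. If these checks show worsening congestion, falling renal function or a significant electrolyte disturbance, a change of diuretic dose is a usual response. The footnote rules it out unless the patient is severely hypotensive.

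Two things are at stake. The first is patient care: an investigator has two instructions that disagree and, on the stricter one, waits for the sponsor before making a non-emergency change. The second is interpretation. Stable diuretics help attribute 1-month changes in NYHA class, walk distance, SF-12 and KCCQ to the device in a study without a control arm. Permitted or not, diuretic changes in this period should therefore be visible beside those results, and the SAP plans no summary of them.

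**Working it through.** The point is textual, and the plan gives no figure to reproduce. The check sets the provisions side by side and then bounds the exposure.

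**1. Does any other text permit the change?**
- *Protocol 12.2* calls for appropriate treatment of adverse events. It is general and does not refer to the footnote, so it conflicts with the footnote without clearly overriding it.
- *Protocol 12.3* exempts laboratory findings from reporting only when they are neither clinically significant nor in need of correction. Significant renal and electrolyte findings therefore remain adverse events to which 12.2 applies.
- *Protocol 14.3, emergency clause*, waives prior approval in an emergency but not reporting.
- *Protocol 14.3, unforeseen circumstances*, relaxes prior approval for matters outside the investigator's control. Its example is a missed visit, and the event still counts as a deviation. A dose change is the investigator's own decision.
- *Protocol 8.4* says that alternative antithrombotic regimens are not deviations. The protocol thus writes a medication carve-out when it means one, and there is none for diuretics.
- *Protocol 18, Heart Failure entry*, mentions increased heart failure therapy when defining a hospitalization. That classifies an event and does not authorise outpatient escalation.

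What remains is the non-emergency change for worsening heart failure or for a clinically significant renal or electrolyte adverse event. There the footnote with 14.3 points to prior approval and a reportable deviation, while 12.2 points to treatment.

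**2. Who is bound, and for how long?**
- Patients under Rev L and after: 30 of 60 (SAP 4). Whether earlier protocol versions carried the rule is not shown.
- Taking 3 months as 90 days and assuming full follow-up: 30 × 90/365 = 7.4 patient-years.
- Share of these patients' first year: 90/365 = 24.7%.
- Share of total planned follow-up: 7.4 / (60 × 3) = 7.4/180 = 4.1%.
- If earlier versions had the same rule: 60 × 90/365 = 14.8 patient-years.

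**3. How many might need a change?** The documents give no rate. Assuming 5%, 10% or 20% of 30 patients gives 30 × 0.05 = 1.5, 30 × 0.10 = 3 and 30 × 0.20 = 6 patients. This is assumed need for any diuretic change, with nothing deducted for emergencies or for prompt approval. It does not count delayed treatments.

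**4. Which results fall in the window?** The 1-month visit is 30 ± 7 days, that is days 23 to 37, wholly before day 90. The 6-month visit (days 150 to 210, SAP 5.2) is after it.

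**5. Would a later admission count?** The Hospitalization/Rehospitalization entry in Protocol 18 counts any unplanned admission, including an emergency department visit. It accepts a CHF hospitalization only with a stay of at least 24 hours, intravenous or mechanical heart failure therapy, and primary heart failure. A shorter stay, oral escalation alone or secondary heart failure would not qualify under that entry.

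**The case against.** The strongest reply is that an investigator who adjusts a diuretic to treat an adverse event is following Protocol 12.2 and so is not deviating. Emergencies are covered by 14.3. Otherwise the investigator contacts a Clinical Affairs representative, and nothing suggests that the answer is slow. Protocol 8.9 also allows withdrawal in the patient's interest. The footnote restricts diuretics only, so other treatment, such as electrolyte correction, stays open. Holding diuretics fixed is a deliberate choice with a sound purpose, and a loose exception could swallow the rule in patients who all enter with symptomatic severe regurgitation. Finally, the documents do not show that any patient is still inside the 3-month window.

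Much of this stands. Because 12.2 and the footnote disagree, deviation status is the stricter reading and is not settled. The stable-diuretic default should stay, and an exception for volume overload without definition would be too broad. What does not fall away is the conflict itself: no text tells the investigator which instruction prevails, and withdrawing a patient in order to adjust a dose loses follow-up.

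A reader might go further and infer that the protocol forbids necessary treatment, that all 60 patients are bound, or that the rule inflates the heart failure re-hospitalization results. The documents do not support these. Emergency care is open; the rule is shown only for Rev L and after; and an admission after a delayed escalation would not automatically meet the CHF definition.

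**Conclusion.** The point holds as a conflict between the footnote and Protocol 12.2, with a patient-care consequence on the stricter reading: prior sponsor approval and a reportable deviation for a non-emergency diuretic change made for worsening heart failure or for a clinically significant renal or electrolyte adverse event. It is worth correcting because the change is small and keeps the design intent. It does not threaten the validity of the study.

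The rule is shown to bind about 30 patients for at most 7.4 patient-years, on the assumptions of 90 days and full follow-up. No approval time and no rate of need are stated, so neither delay nor harm can be sized, and the effect on re-hospitalization cannot be estimated. The patient-year figures and the 1.5 to 6 patients describe the length of the window and assumed need only.

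**What to change.** Keep stable diuretics as the default. In the three footnotes, replace the exception with: *unless medically required to treat severe hypotension, or an adverse event of worsening heart failure (new or worsened signs or symptoms compared with discharge), renal dysfunction or electrolyte disturbance that is clinically significant; such changes do not need prior sponsor approval, and the date, dose and reason must be recorded.* Anchoring worsening to the discharge state keeps the exception from covering the congestion with which patients entered.

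In SAP 8.4.2, add a listing of diuretic changes before day 90, built from the concomitant medication and dose data. Give date and reason where recorded, and include pre-Rev-L patients only where comparable data exist. Show it beside the 1-month NYHA, walk distance, SF-12 and KCCQ results and the heart failure re-hospitalization results.

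The cost is an edit to three footnotes, one listing and up to a few CRF fields. The protocol's tables specify medications and doses but not the date of or reason for a change, and no visit is scheduled between day 37 and day 150. Diuretic therapy would be slightly less uniform in the first 3 months, which the listing makes visible. The wording change helps only patients still inside their window when it takes effect; the listing is useful either way.
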